could have a considerable impact on the budget for antiretroviral treatment within the policy of containing health expenditure promoted by the Spanish health authorities and more necessary today than ever in the current context of economic crisis (18). In addition, it can help reduce your already low risk of chronic toxicity. Finally, dose reduction is considered a popular measure and positively evaluated by a high proportion of treated patients. If our project obtains favorable results that support the dosage reduced to three days per week, the experimental regimen would become the simplest and cheapest among all the currently available regimens, including monotherapy with protease inhibitors.

Determination of plasma viral load and CD4 and CD8 cell counts have been key tools for clinical research and healthcare of HIV-positive patients until now. However, in patients with persistently undetectable viral load and relatively high CD4 counts, the simple determination of viral load and cell populations is unlikely to allow a fine distinction between the possible virological and immunological consequences of the dose reduction strategy to be evaluated. Therefore, viral reservoir analysis by determining proviral DNA and especially the proportion of that reservoir that produces viral particles can provide more detailed information on the virological safety of the new strategy (19). Similarly, the determination of plasma viral load using the most sensitive technique ("single copy assay" (limit of detection 1 copy/mL) (20) can discriminate whether this dose-reduction strategy produces any impact on viral replication that cannot be detected by the standard technique used in routine clinical practice. On the other hand, the extensive immunological study that is intended to be carried out (population analysis of the T lineage that includes its activation status and thymic production, among others) will allow us to exhaustively monitor the effects of any changes that may occur at this level on the study population (21-23). Therefore, we consider that the efficacy and safety of the dose reduction strategy of the efavirenz/tenofovir/emtricitabine regimen should be evaluated as consistently as possible with the previously mentioned virological and immunological tests.

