6.1 Primary and Secondary Endpoints**Primary Endpoint:**

The primary endpoint of the study will be the proportion of patients who continue to have a standard plasma viral load (<37 copies/mL) at 24 weeks by intention-to-treat analysis.

Secondary endpoints:

- 1) The proportion of patients with ultrasensitive viral load (<1 copy/mL) after 24 weeks.
- 2) The change from baseline to 24 weeks in the viral reservoir of peripheral blood mononuclear cells
- 3) Changes from baseline to 24 weeks in TREC production, immune profile of activation (CD38 and HLA-DR) and senescence (CD57 and CD28) in CD4 and CD8 lineages, in naïve and effector and memory T cell ratios (CCR7 and CD45RA), and changes in apoptosis levels in vitro by annexin V staining.
- 4) Changes in plasma levels of efavirenz.
- 5) Changes in sleep quality (Pittsburgh Sleep Quality Index), plasma levels of vitamin D and lipids, and estimated glomerular filtration rate.
- 6) Overall safety (reporting side effects, serious side effects, and discontinuation of treatment due to side effects)

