6.2 Design

Although the hypothesis of the study has been based on various congruent information that allow us to face with sufficient guarantee the feasibility of the study and the eventual demonstration of the virological and immunological efficacy of the ATRIPLA® dose reduction strategy, we are not absolutely certain that an unacceptably high virological failure rate (standard viral load ≥ 37 copies/mL on two consecutive occasions) can occur in the arm

experimental. We will consider a priori that the failure of at least 20% (n=6) of the patients in the experimental arm will represent an unacceptably high virological failure rate. In this case, its conclusion will be considered premature. In this extreme case, the data of the patients already included up to the time of the premature conclusion of the study would be analyzed.

The present study is proposed as a proof of concept to be able to formulate another study with a sufficiently large sample size to adequately demonstrate the non-inferiority of the strategy. The results of the present study can help to design the non-inferiority study and to estimate its sample size.

STUDY PROCEDURES

Selection Evaluations								
Clinical Evaluations		Selection						
Informed consent								X
Inclusion and exclusion criteria								X
Assignment of the selection code								X
Vital signs								X
Weight Determination								X
Height determination								X
Demographics								X
Medical history								X
Physical examination								X
Concomitant medications								X
Confirmation of the use of contraceptive methods by the patient and his or her partner								X

Clinical Evaluations	Basal Day 0	S 1 (#)	S 2 (#)	S 4 (#)	S 6 (#)	S 8 (#)	S 12	S 24
Meet Inclusion and Exclusion Criteria	X							
Signed Informed Consent	X							
Vital signs	X							
Weight	X							X
Physical examination	X						X	X
Adverse events		X	X	X	X	X	X	X
Concomitant medications	X	X	X	X	X	X	X	X
Simplified Compliance Questionnaire		X	X	X	X	X	X	X
Test sobre calidad del sueño (Pittsburgh Sleep Quality Index)	X							X
Haematology	X							X
Blood biochemistry	X							X

Clinical Evaluations	Basal Day 0	S 1 (#)	S 2 (#)	S 4 (#)	S 6 (#)	S 8 (#)	S 12	S 24
Standard plasma viral load	X	X	X	X	X	X	X	X
Ultrasensitive plasma viral load (\$)	X							X
HIV-1 reservoir of PBMCs	X							X
Immunology (CD4/CD8)	X						X	X
Immunology Sample	X							X
Pregnancy test (women only) Y(&)	X	X	X	X	X	X	X	X
Pharmacokinetics	X							X

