All laboratory specimens should be obtained prior to administration of the first dose of study medication.

(#) These visits will be made only to patients who are in the experimental treatment arm (3-day-per-week treatment)

& At baseline visit it is advised to perform a blood pregnancy test

* Genotypic resistance testing will be performed if the patient has virologic failure (defined by HIV-1 plasma viral load >50 copies/mL confirmed on two consecutive occasions)

Blood biochemistry: lipids (TG, total cholesterol and HDL), creatinine and estimated glomerular filtration rate (CPK-EPI), levels of 25OH vitamin D.

Hematology: Blood count

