7.1 Inclusion criteria for subjects

A patient must meet ALL of the criteria listed below in order to participate:

1. Adults (≥ 18 years)
2. HIV-1 infection, clinical stability, and treatment with ATRIPLA® during the last two years.
3. Standard plasma viral load below the detection limit for at least the last 2 years.
4. CD4 count greater than 350/mm³ at the time of study consideration.

5. Negative pregnancy test in women of childbearing potential, and commitment to use acceptable contraceptive methods from at least 2 weeks before day 1 and until at least 6 months after the last dose of study drug.
6. Patients must have given written informed consent
7. In the opinion of the researcher, to be able to follow the design of the protocol visits.

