10.1 Detection and recording of Adverse Events

It is the investigator's responsibility to detect and document any event that meets the criteria and definitions of adverse event (AE) or serious adverse event (SAE) as set forth in this protocol. During the study, the existence of adverse events, whether serious or not, will be checked in accordance with the definition given in this section of the protocol.

a) Minimum information to be specified:

Description/definition:

Adverse event (AE) is any adverse health event in a patient or clinical trial subject treated with a medicine, even if it is not necessarily causally related to that treatment. Therefore, it can be any unfavorable and unintended signs (including an abnormal laboratory finding), symptom, or illness temporarily associated with the use of an investigational drug, whether or not related to the investigational drug.

Laboratory abnormalities of clinical importance that meet one or more of the following criteria are also considered AEs:

- It requires additional intervention or treatment.
- Requires a modification of the dose.

- It is accompanied by a clinical manifestation.

Any analytical anomaly that the investigating physician considers to be of clinical importance must be recorded as such in the printed copy of the laboratory report, indicating the physician's initials and the date of revision. An AA is also considered to be any event associated or observed in conjunction with an accidental or intentional overdose of the product, or with abuse or withdrawal of the product.

All AEs will be recorded in the subject's medical record and in the eCRDe. The start and end dates of each AA, the intensity and the relationship with the study drug will be recorded.

The criteria for subject treatment, dose discontinuation, dosage adjustment, withdrawal, or treatment changes will only apply to toxicities attributable to the study drugs (i.e., efavirenz, tenofovir, and emtricitabine).

The classification system for drug toxicity is set out in the DAIDS Table for Grading the Intensity of Adverse Events in Adults and Children, which can be found on the DAIDS RSC website: <http://rsc.tech-res.com/safetyandpharmacovigilance/>.

In addition, for each AA, the measures taken or the outcome (e.g. hospitalization, discontinuation of treatment) will be recorded.

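### Secondary endpoint 6 has no Day 0 side-effect record and no rule for symptoms ongoing at entry, so improvement in existing symptoms outside endpoint 5 is not systematically documented and old symptoms can be logged as on-study events

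*Combined protocol and SAP*

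**What the plan says.** Section 6.1 lists as secondary endpoint 6 "Overall safety (reporting side effects, serious side effects, and discontinuation of treatment due to side effects". It is not worded as a change. The endpoint before it is: "Changes in sleep quality (Pittsburgh Sleep Quality Index), plasma levels of vitamin D and lipids, and estimated glomerular filtration rate". General tolerability is part of the safety objective in sections 1.10.2 and 5, with no instrument or time point attached.

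Section 7.1 admits patients with "HIV-1 infection, clinical stability, and treatment with ATRIPLA® during the last two years". No criterion requires freedom from side effects.

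In the schedule (section 6.2, repeated in section 17) the row "Adverse events" is marked at S1, S2, S4, S6, S8, S12 and S24 and blank at Day 0. Concomitant medication, the sleep index, haematology and biochemistry all have a Day 0 mark. The selection visit includes medical history and physical examination but no side-effect record. On S1 to S8 the footnote says: "These visits will be made only to patients who are in the experimental treatment arm (3-day-per-week treatment".

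Section 10.1 asks for start and end dates of each event, and "the intensity and the relationship with the study drug will be recorded", with grading on the DAIDS table. Section 4 mentions toxicity among the expected gains: "In addition, it can help reduce your already low risk of chronic toxicity".

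**The concern.** The experimental arm takes less of a drug that all patients already take. One plausible effect is that an existing complaint eases. Showing this needs a record of the complaint and its grade before the switch, and none is scheduled.

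The same gap affects the count of events. With no rule for symptoms present at entry, one complaint may be left out, dated to before entry, or entered as an on-study event, depending on who asks and what the patient recalls. Controls are first asked at S12, so their onset dates rest on twelve weeks' recall. Experimental patients are asked from week 1.

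At stake is whether the pilot can describe tolerability on the reduced schedule well enough to inform the larger trial it is meant to prepare. The pre-switch state cannot be reconstructed reliably afterwards.

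**Working it through.** The plan gives no figure for tolerability to reproduce. The check is a reading of the schedule plus arithmetic on assumed rates.

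**1. Arm size.** Sections 6.2 and 11.3 equate 20% of the experimental arm with 6 patients: 6 / 0.20 = 30, which agrees with 60 / 2 = 30.

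**2. Scheduled adverse-event enquiries.**

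| | Day 0 | S1–S8 | S12, S24 | After Day 0 |
|---|---|---|---|---|
| Experimental | 0 | 5 | 2 | 7 |
| Control | 0 | 0 | 2 | 2 |

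**3. What has a starting value.** Sleep index, lipids, vitamin D and eGFR are taken at Day 0 and S24 in both arms and analysed as changes. Other complaints, for example dizziness, mood or gastrointestinal symptoms, have no scheduled graded value before the switch.

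**4. Effect of 7 against 2 enquiries.** Let q be the chance that one enquiry yields a record, equal in both arms and independent between visits (assumption). The chance of at least one record is 1 − (1 − q)^k, with k = 7 or 2. The last column is the chance that Fisher's exact test (two-sided 5%, assumed; 30 per arm) is significant when the arms do not truly differ.

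| q | Experimental | Control | Significant |
|---|---|---|---|
| 0.05 | 30% | 10% | 39% |
| 0.10 | 52% | 19% | 70% |
| 0.20 | 79% | 36% | 90% |
| 0.30 | 92% | 51% | 94% |

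All these false positives count against the reduced schedule. Independence suits episodic complaints. A constant symptom that is reported whenever asked about would be caught by two enquiries as well as by seven, so the imbalance would shrink. With S12 and S24 only, k = 2 in both arms and the expected shares are equal.

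**5. What a Day 0 record could show.** Assume a share π of patients has a symptom at Day 0, and that it resolves by week 24 in 10% on daily dosing and in a share r on reduced dosing. Week 24 prevalence is then π × 0.9 in controls and π × (1 − r) in the experimental arm. Fisher power at 30 per arm:

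| π | Symptomatic per arm | r = 50% | r = 80% |
|---|---|---|---|
| 10% | 3 | 1% | 3% |
| 20% | 6 | 6% | 21% |
| 30% | 9 | 13% | 46% |
| 40% | 12 | 20% | 68% |
| 50% | 15 | 27% | 83% |

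Testing only patients symptomatic at Day 0 does no better. With 6 to 12 per arm and improvement of 50% against 15% (assumed), power is about 5% to 30%. Results of 3/6 against 1/6 and 6/12 against 2/12 give p = 0.55 and p = 0.19.

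**The case against.** A reader might infer that the trial cannot show relief of side effects at all. The documents do not support this. Endpoint 5 measures change in sleep and three laboratory markers, and eGFR addresses the progressive renal toxicity named in section 4.

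A reader might also infer that endpoint 6 counts only new events. Section 10.1 has no new-onset restriction and records start and end dates, so an old symptom can be dated before entry and its end noted if someone reports it. Medical history may hold some symptoms, and the list of CRD variables in Annex VI is not in the text available. What stands is that the capture is unsystematic.

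Nor is relief of symptoms presented as the main benefit. Section 4 leads with a 57% cut in expenditure and simpler dosing. Toxicity comes second, and the sentence concerns the risk of chronic toxicity rather than current complaints.

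It is tempting to say that the endpoint would drift towards no difference. Loss of improvements from the record does point that way, but the unequal enquiries push towards more recorded events on the reduced schedule.

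The strongest objection is that little may be left to relieve. Section 4 describes the neuropsychological effects as generally mild and often gone after the first month, and section 7.1 requires clinical stability. This stands. It argues for a descriptive report and against a formal test. It does not remove the risk of misclassifying the symptoms that do exist.

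**Conclusion.** The concern holds in a limited form. Endpoint 6 lacks a scheduled Day 0 side-effect record and a rule for symptoms ongoing at entry. Apart from the endpoint 5 measures, improvement is not systematically documented, and a long-standing symptom may be counted as an on-study event, more readily in the experimental arm.

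The gap and the 7 against 2 count come directly from the schedule, and both copies of the table agree. The sizes rest on assumptions, because the documents give no symptom prevalence, resolution rate or reporting rate. On those assumptions, unequal enquiry alone could produce a significant excess of events in the experimental arm 39% to 94% of the time. A formal test of relief would have 1% to 27% power if half of the symptoms resolved, and 3% to 83% if four fifths did. This is a worthwhile, inexpensive improvement to a secondary endpoint. It does not affect the primary endpoint.

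**What to change.** - Mark the adverse-event row at Day 0 in the tables of sections 6.2 and 17, for both arms. Record current symptoms with their DAIDS grade before the allocation is disclosed.
- State in section 10.1 how a symptom ongoing at Day 0 is handled.
- Report endpoint 6 in two parts: (a) events new or worse than the Day 0 grade; (b) Day 0 symptoms improved or resolved.
- Compare arms on both parts using only what is solicited at S12 and S24, with the same question and recall period in each arm. List reports from S1 to S8 separately for the experimental arm.
- Label part (b) descriptive: counts with confidence intervals, no claim from a test.

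The cost is a few minutes per patient at an existing visit and one extra eCRD page. There is no added visit, test or patient, and no change to treatment. The reports remain subjective in an open-label trial, and restricting the comparison to two visits leaves transient early complaints out of it, though they stay in the listing.

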6.2 Design

Although the hypothesis of the study has been based on various congruent information that allow us to face with sufficient guarantee the feasibility of the study and the eventual demonstration of the virological and immunological efficacy of the ATRIPLA® dose reduction strategy, we are not absolutely certain that an unacceptably high virological failure rate (standard viral load ≥ 37 copies/mL on two consecutive occasions) can occur in the arm

experimental. We will consider a priori that the failure of at least 20% (n=6) of the patients in the experimental arm will represent an unacceptably high virological failure rate. In this case, its conclusion will be considered premature. In this extreme case, the data of the patients already included up to the time of the premature conclusion of the study would be analyzed.

The present study is proposed as a proof of concept to be able to formulate another study with a sufficiently large sample size to adequately demonstrate the non-inferiority of the strategy. The results of the present study can help to design the non-inferiority study and to estimate its sample size.

STUDY PROCEDURES

Selection Evaluations								
Clinical Evaluations		Selection						
Informed consent								X
Inclusion and exclusion criteria								X
Assignment of the selection code								X
Vital signs								X
Weight Determination								X
Height determination								X
Demographics								X
Medical history								X
Physical examination								X
Concomitant medications								X
Confirmation of the use of contraceptive methods by the patient and his or her partner								X

Clinical Evaluations	Basal Day 0	S 1 (#)	S 2 (#)	S 4 (#)	S 6 (#)	S 8 (#)	S 12	S 24
Meet Inclusion and Exclusion Criteria	X							
Signed Informed Consent	X							
Vital signs	X							
Weight	X							X
Physical examination	X						X	X
Adverse events		X	X	X	X	X	X	X
Concomitant medications	X	X	X	X	X	X	X	X
Simplified Compliance Questionnaire		X	X	X	X	X	X	X
Test sobre calidad del sueño (Pittsburgh Sleep Quality Index)	X							X
Haematology	X							X
Blood biochemistry	X							X

Clinical Evaluations	Basal Day 0	S 1 (#)	S 2 (#)	S 4 (#)	S 6 (#)	S 8 (#)	S 12	S 24
Standard plasma viral load	X	X	X	X	X	X	X	X
Ultrasensitive plasma viral load (\$)	X							X
HIV-1 reservoir of PBMCs	X							X
Immunology (CD4/CD8)	X						X	X
Immunology Sample	X							X
Pregnancy test (women only) Y(&)	X	X	X	X	X	X	X	X
Pharmacokinetics	X							X

All laboratory specimens should be obtained prior to administration of the first dose of study medication.

(#) These visits will be made only to patients who are in the experimental treatment arm (3-day-per-week treatment)

& At baseline visit it is advised to perform a blood pregnancy test

* Genotypic resistance testing will be performed if the patient has virologic failure (defined by HIV-1 plasma viral load >50 copies/mL confirmed on two consecutive occasions)

Blood biochemistry: lipids (TG, total cholesterol and HDL), creatinine and estimated glomerular filtration rate (CPK-EPI), levels of 25OH vitamin D.

Hematology: Blood count

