6.6 Termination and/or discontinuation criteria

The treatment will be **compulsorily** terminated during the study for any of the following reasons:

- Virologic failure, defined by two consecutive determinations of standard viral load >37 copies/mL separated by one week from each other.
- I express the patient's wish.
- Medical decision.
- Death.
- Pregnancy detection during the study.

Treatment **may** be terminated during the study for any of the following reasons:

- The medical investigator determines that a SAE is possibly or likely related to the study drug.
- Failure to administer, evaluate, or other study requirements.

If the confirmatory result is ≥ 37 copies/mL, a genotypic resistance detection study would be scheduled and the most appropriate attitude towards modifying their antiretroviral treatment would be discussed with the patient. In this case, unless he or she is against it, the patient would continue in the study.

All other virologic studies and immunological studies should be determined exclusively at baseline and 24 weeks (except if there is earlier virologic failure, in which case it would be performed at the time of confirmation of failure rather than at 24 weeks), and their determination should be deferred at the end of the study. To this end, plasma and peripheral blood mononuclear cell samples should be stored appropriately at -80°C until the planned determinations are made.

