10.2. Notification

The investigator or designee **must notify all AAGs, regardless of whether or not they are considered drug-related or planned**, to the head of the CTU. [name] ([contact]) [contact] [name] [REDACTED] in order to notify local and national health authorities **within one working day of becoming aware of the event**, so that the contact of the designated promoter can prepare the corresponding written report. AAGs occurring will be reported at any time from the subject's inclusion in the study and up to 30 days after the study has been completed or discontinued. In the specific case of selection failure, the AAGs will be recorded from the moment the consent is signed until the subject is considered a selection failure.

Regardless of the classification of adverse effects, the Investigator must collect all the AEs in the corresponding section of the study data collection notebook (CRD) and fill in all the information pertaining to them.

The sponsor must notify in an EXPEDITIOUS manner all relevant SAFETY INFORMATION, i.e. that could modify the risk/benefit ratio of the investigational medicine, or determine changes in its administration schedule or in the conduct of the trial, for example:

- a qualitative change or an increase in the percentage of occurrence of expected RAGs, which is considered clinically important.
- RAGIs that occur after the completion of a clinical trial and that are notified by the investigator to the sponsor.
- New developments related to the conduct of the trial or the development of the investigational medicinal product and likely to affect the safety of the subjects, such as:
 - Serious adverse events that may be associated with the trial procedures and may modify the conduct of the trial
 - A significant risk to subjects such as the lack of efficacy of an investigational drug used for the treatment of a life-threatening disease.
 - Important new safety findings from new animal studies (such as cardiogenicity).
 - Any premature termination or temporary halt of a clinical trial with the same investigational medicinal product for safety reasons, carried out in another country and by the same sponsor.
 - GRAs related only to an MNI that are considered relevant as they are not subject to RAGI's general rules of expedited reporting of individual cases.
- Any recommendations from the data monitoring committee, which are relevant to the safety of the subjects.

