10.4 COMMUNICATION TO RESEARCHERS

The sponsor shall communicate to investigators any information that may affect the safety of the trial subjects as soon as possible.

It is advisable when deemed appropriate that information on serious and unexpected adverse reactions (RAGI) be presented in a list together with a brief analysis of the data provided.

Researchers must also be informed of the safety aspects that impact the conduct of the clinical trial or the development of the product. Including disruption of the development program or security-related protocol modifications.

Follow-up of subjects after adverse events will be performed by clinical and complementary examinations necessary for the duration of treatment and then on a monthly basis during follow-up and up to 30 days after the end of treatment. In the event of a possible pregnancy, the health status of both the mother and the newborn will be monitored during the trial, whether the person who has become pregnant is the one who is taking the investigational drug or if it has been taken by her partner.

No interim analyses are planned for the present study.

11. Statistics

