11.2 Sample size

11.3 Analysis

Comparison of patient proportions will be performed using Fisher's exact test and the 95% confidence interval will be calculated for the difference in proportions.

Quantitative data at baseline and after 24 weeks, as well as absolute and relative changes at 24 weeks, will be compared using the Wilcoxon rank sum test. The point estimate and 95% confidence interval of the difference in medians will be estimated using the Hodges-Lehman methodology using the Moses free distribution.

Correlations between continuous variables will be evaluated using Spearman's rank correlation test.

The study of baseline predictors of response will be carried out by means of a multivariate analysis of multiple logistic regression.

Limitations of the study:

Although the hypothesis of the study has been based on various congruent information that allow us to face with sufficient guarantee the feasibility of the study and the eventual demonstration of the virological and immunological efficacy of the ATRIPLA® dose reduction strategy, we are not absolutely certain that an unacceptably high virological failure rate (standard viral load ≥ 37 copies/mL on two consecutive occasions) may occur in the experimental arm. We will consider a priori that the failure of at least 20% (n=6) of the patients in the experimental arm will represent an unacceptably high virological failure rate. In this case, its conclusion will be considered premature. In this extreme case, the data of the patients already included would be analyzed.

This study, even with the most favorable virologic and immunological results, would not constitute definitive proof of the safety and efficacy of ATRIPLA®'s dose reduction strategy. The present study is only a proof of concept and another study with a sufficiently large sample size would be needed to adequately demonstrate the non-inferiority of the strategy. The results of the present study can help to design the non-inferiority study and to estimate its sample size.

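### Adverse events are asked about at 7 post-baseline visits in the experimental arm and 2 in control, so a pooled 24-week comparison of non-serious side effects is not like for like

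*Combined protocol and SAP*

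**What the plan says.** The procedures tables in sections 6.2 and 17 mark adverse events at weeks 1, 2, 4, 6, 8, 12 and 24. Weeks 1 to 8 carry the (#) sign, explained as: "These visits will be made only to patients who are in the experimental treatment arm (3-day-per-week treatment". Weeks 12 and 24 apply to both arms.

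Section 6.1 lists as secondary endpoint 6: "Overall safety (reporting side effects, serious side effects, and discontinuation of treatment due to side effects". Section 11.3 does not name adverse events. Its only method for proportions is Fisher's exact test, and it adds that "the 95% confidence interval will be calculated for the difference in proportions". It does not restrict any comparison to visits that both arms share, and its limitations text does not mention the unequal schedule.

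Three other provisions bear on the point:
- Section 10.1, on each adverse event: "The start and end dates of each AA, the intensity and the relationship with the study drug will be recorded".
- Section 10.2, on serious adverse events (abbreviated AAG in the translation): "AAGs occurring will be reported at any time" from inclusion to 30 days after the study has been completed or discontinued.
- Section 10.4: "Follow-up of subjects after adverse events will be performed by clinical and complementary examinations necessary for the duration of treatment". This starts once an event is known.

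**The concern.** A mild, short event is more likely to be reported if someone asks soon after it happens. Up to week 12 the experimental arm is asked six times and control once. No telephone call, diary or other contact is scheduled for control in its place, and the follow-up in section 10.4 does not help with first detection.

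If more non-serious events appear on the reduced schedule, a reader could not separate a real excess from more frequent asking. If the reduced schedule truly lowers side effects, the imbalance would tend to mask it. The justification section hopes for lower toxicity, and the study is meant to inform a later non-inferiority trial, so a distorted tolerability picture could carry forward.

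The concern covers non-serious events that are short and not fully recalled. Laboratory measures, the sleep index and the week-24 viral load are taken at visits both arms have. The primary endpoint is not involved.

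**Working it through.** The plan states no figure for this, so there is none to reproduce. The counts are exact; everything after step 2 is illustrative.

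**1. Visits (tables and footnote, sections 6.2 and 17).** Experimental: weeks 1, 2, 4, 6, 8, 12, 24 = 7. Control: weeks 12, 24 = 2. Up to week 12 this is 6 v 1; after week 12 it is 1 v 1.

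**2. Mean wait from onset to the next check.** With onset uniform over an interval, the mean wait is the sum of squared gaps divided by twice the interval length. Up to week 12 the experimental gaps are 1, 1, 2, 2, 2 and 4 weeks:
- Experimental: (1 + 1 + 4 + 4 + 4 + 16)/(2 × 12) = 30/24 = 1.25 weeks.
- Control: 12²/(2 × 12) = 144/24 = 6.0 weeks.
- Weeks 12 to 24: 6.0 weeks in both arms.

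**3. Share of events reported under gradual forgetting.** Assumptions, none from the documents: the same true rate in both arms, onset uniform over 24 weeks, and an event reported at the next check with probability 0.5^(wait/H), where H is a recall half-life in weeks. A gap of g weeks then contributes (H/ln 2) × (1 − 0.5^(g/H)), and the sum over gaps is divided by 24.

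For H = 4, H/ln 2 = 5.771:
- Experimental (gaps 1, 1, 2, 2, 2, 4, 12): 5.771 × (2 × 0.159 + 3 × 0.293 + 0.500 + 0.875)/24 = 0.618.
- Control (gaps 12, 12): 5.771 × (2 × 0.875)/24 = 0.421.
- Ratio: 0.618/0.421 = 1.47.

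| Half-life (weeks) | Experimental | Control | Ratio, 24 weeks | Ratio, weeks 0–12 | Ratio, weeks 12–24 |
|---|---|---|---|---|---|
| 2 | 0.459 | 0.237 | 1.94 | 2.88 | 1.00 |
| 4 | 0.618 | 0.421 | 1.47 | 1.94 | 1.00 |
| 8 | 0.761 | 0.622 | 1.22 | 1.45 | 1.00 |
| 12 | 0.827 | 0.721 | 1.15 | 1.29 | 1.00 |
| Full recall | 1.000 | 1.000 | 1.00 | 1.00 | 1.00 |

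All of the excess arises before week 12.

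**4. A different forgetting rule.** If an event is reported only when it began within R weeks of the next check, the covered onset weeks out of 24 are 12 v 4 (R = 2), 16 v 8 (R = 4), 20 v 16 (R = 8) and 24 v 24 (R = 12). The ratios are 3.0, 2.0, 1.25 and 1.0. The direction is the same; the size depends on the rule.

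**5. What a split at week 12 leaves.** Arm size: section 6.2 refers to "the failure of at least 20% (n=6) of the patients in the experimental arm", so 6/0.20 = 30 per arm out of 60. Take H = 4 and assume 1 event per patient over 24 weeks:
- Share of all events reported with onset after week 12: 5.771 × 0.875/24 = 0.210 in each arm.
- Expected reported events: 30 × 0.210 = 6.3 per arm, against 30 × 0.618 = 18.5 v 30 × 0.421 = 12.6 over the full period.
- Patients with at least one: 1 − exp(−0.210) = 0.19.
- 95% half-width for the difference: 1.96 × √(2 × 0.19 × 0.81/30) = 0.20.

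**6. Why numbers at risk matter.** Suppose 5 experimental patients, one below the threshold of 6, left before week 12 but stayed in the denominator of 30 as event-free. The later-period ratio would be 25/30 = 0.83 with no true difference. With an at-risk denominator it is 1.0, provided leaving is unrelated to events.

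**The case against.** The extra visits are deliberate. They carry viral loads in the arm where section 6.2 fears excess failure, and nobody should want them removed. Section 10.2 tells the investigator to collect all adverse events, and section 10.1 requires start and end dates, which fits asking back over the whole interval; with full recall the bias vanishes. The direction is conservative for the new schedule, and the protocol disclaims definitive proof of safety. All of this stands, and it keeps the point small. Recorded dates cannot, however, recover an event that was never reported.

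A reader might go further and infer that the plan has an inflated false-positive rate for side effects. The documents do not support that. Section 11.3 never says adverse events will be tested; if safety is only tabulated, no error rate exists. If Fisher's test were applied to patients with at least one event over 24 weeks, 30 per arm, the rejection rate with no true difference at 1 event per patient would be 18.8%, 9.7%, 5.1% and 3.8% for half-lives of 2, 4, 8 and 12 weeks. At 0.25 events per patient it is 2.2% to 2.5%, against 2.4% with full recall, so there is no real inflation. The estimate would still be shifted: at that rate and H = 4, about 14% v 10% of patients would report an event. The event rate and the recall are assumptions throughout.

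A reader might also infer that all formal comparison must be confined to the period after week 12. That is too strict. It would leave the weeks just after the switch without any formal look, it rests on a group defined after randomisation, and with H = 4 and 1 event per patient it has about 19% power to detect a true doubling of the later-period rate.

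Finally, it is fair to object that serious events and discontinuations are not wholly immune. Section 10.2 sets a reporting duty on becoming aware of an event and schedules no contact that creates awareness, and a discontinuation can be prompted at an extra visit.

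**Conclusion.** The point holds as a minor design and reporting matter. The 7 v 2 count is exact, and nothing in the documents offsets it. With any incomplete recall, a pooled 24-week comparison of non-serious side effects leans towards more mild, short events in the experimental arm. The size is unknown: 1.94 to 1.15 as a capture ratio for assumed half-lives of 2 to 12 weeks, and 1.0 with full recall. These figures rest on uniform onset and equal true rates. The secure conclusion is a biased comparison of unknown size, not a particular error rate.

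It affects one component of the sixth secondary endpoint in a 60-patient proof of concept. Under section 6.3, grade 1 and 2 events change no treatment.

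**What to change.** Keep all visits. Add to section 11.3:
- Non-serious adverse events are reported by randomised arm in two periods, by recorded start date: baseline to the week-12 visit, and after the week-12 visit to week 24. Numbers at risk and numbers off assigned treatment are shown by arm.
- The later period, where both arms have the same single check, is the like-for-like comparison. The weeks 0–12 and full 24-week figures are descriptive, and no difference in them is attributed to treatment.
- Serious events and discontinuations due to side effects are reported over the full 24 weeks, with a note that discontinuations may also be prompted at the extra visits.

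Add to the limitations that adverse events were asked about at 7 visits in the experimental arm and 2 in control.

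The two counts by arm are needed because the week 1 to 8 viral loads exist only in the experimental arm, so confirmed failure can end treatment earlier there. Section 6.6 also says that after confirmed failure, "unless he or she is against it, the patient would continue in the study", so follow-up and treatment status are different things. Section 11.5 analyses available data only.

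The cost is wording; start dates are already recorded, and no visit or patient question is added. The price is precision: about 6 events per arm and an interval of about ±20 percentage points in the case worked above. The later comparison depends on who is still followed at week 12. It also does not remove any greater readiness to report that the extra visits may have created in the experimental arm.
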